At the time of randomization to vaccine allocation, women will also be randomized to a schedule of postpartum visits for specimen collection. All women-infant pairs will have specimens collected at birth, at 6 weeks after delivery, and at 6 months after delivery. In addition, women-infant pairs will be allocated in a 1:1 ratio to have specimen collections at one month following the first dose of DTwP (approximately 10 weeks of age), or at one month following the third dose of DTwP (approximately 18 weeks of age). Thus, pregnant subjects will typically have 7 clinic visits (only 6 if delivery occurs before the first visit after vaccination, on Day 31): 3 antenatal visits (Screening Visit, Study Day 1, and Study Day 31, unless delivery occurs first), 1 visit at the time of delivery, and 3 postpartum visits – at 6 weeks, at 10 or 18 weeks postpartum, and a final visit 6 months postpartum. The maternal subject will also undergo 2 home visits after vaccination to assess her health status (Days 4 and 8). Infants born to the pregnant subjects will have 4 study visits: at birth, at approximately 6 weeks of age (day of first DTwP), at approximately 10 or 18 weeks of age (one month after first or third dose of DTwP, respectively), and at 6 months of age. Blood and colostrum/breast milk samples for immunologic assessments will be collected as described below:

- Pregnant subjects: approximately 30 mL of whole blood will be collected by venipuncture on Study Day 1 (prior to vaccination), Study Day 31 (one month after vaccination), at delivery, and at 6 months postpartum in all women.
- Infants: up to 30 mL of umbilical cord blood will be collected at delivery and 5 mL peripheral blood will be collected by venipuncture at 6 weeks (prior to first dose of DTwP), either the 10-week or 18-week (per randomized study schedule), and 6 months of age in all infants. If cord blood cannot be obtained, 2-5 mL of peripheral blood will be collected by venipuncture within 72 hours of birth when possible. Cord blood is preferred over venipuncture.

- At delivery, and at the 6-week, either the 10-week or 18-week (per randomized study schedule), and the 6-month postpartum visit, a 10-20mL sample of colostrum or breast milk will be collected. When possible, the first breast milk or colostrum collection will occur while the mother and baby are admitted for delivery and postpartum care. When not possible, it may be collected any time within the first 4 days of life.

[figure not shown]

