The vaccine manufacturer maintains a surveillance registry to collect data on pregnancy outcomes and newborn health status outcomes following vaccination with BOOSTRIX during pregnancy. In the event of an observed safety signal from that registry, the manufacturer would share that information with the sponsor and appropriate actions for trial subjects would be taken. It is unknown if the vaccine to be used in this study poses any risks to an unborn child or to children born to mothers who are vaccinated during pregnancy. The vaccine is currently deemed as pregnancy category B. A developmental toxicity study has been performed in female rats at a dose approximately 40 times the human dose (on a mL/kg basis) and revealed no evidence of harm to the fetus due to BOOSTRIX. Animal fertility studies have not been conducted with BOOSTRIX.

The effects of the vaccine on lactation and nursing, as well as the effects on the breastfed infant of a woman vaccinated with BOOSTRIX during pregnancy, are unknown.

Breast Milk Collection: Women will provide breast milk within the 4 days following delivery and at 3 time points postpartum (at 6 weeks, either 10 or 18 weeks, and 6 months postpartum). There is no significant risk of this collection. Some women may experience mild tenderness from milk expression.

Potential Risks to Infants: As with the risks to pregnant women, there is a possibility that obtaining a blood sample from your infant may cause some pain, swelling, bruising, or infection at the site of the blood draw. To avoid infection, a qualified and trained staff member will collect the blood from the infant.

The standard of care in Mali is to vaccinate infants with the pentavalent Diphtheria and Tetanus and Pertussis and Haemophilus influenzae and Hepatitis B vaccine at 6, 10, and 14 weeks of age; this vaccination should provide protection. There is a possibility that the infant's response to the pertussis vaccine could be lower after the usual infant vaccinations because of the mother's study vaccine.

Privacy and Confidentiality: Subjects will be asked to provide and allow research team members access to personal/protected health information (PHI) of the woman and her infant. All attempts will be made to keep this PHI confidential within the limits of the law. However, there is a chance that unauthorized persons will see subject PHI. All paper records will be kept in a

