3.1.2. Secondary

Immunogenicity:

- To assess the antibody response to BOOSTRIX vaccine antigens in pregnant women one month after receipt of BOOSTRIX, at the time of delivery, and at 6 months after delivery.
- To compare the antibody levels of BOOSTRIX vaccine antigens at birth (cord blood) and 6 weeks of age (before receiving any infant doses of Diphtheria, Tetanus, and whole-cell Pertussis (DTwP)) in infants whose mothers received BOOSTRIX or Td during pregnancy.
- To assess placental antibody transfer by determining the ratio of maternal and infant BOOSTRIX -specific antibody responses at delivery.
- To assess interference with infant antibody responses to DTwP either prior to the second dose of the primary DTwP series, at approximately 10 weeks of age (in ½ of subjects), or approximately one month after the third dose of the primary DTwP series, at approximately 18 weeks of age (in ½ of subjects), and at 6 months of age (all subjects).

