3.2.2. Secondary

Immunogenicity:

- Maternal humoral immunity: GMC of serum IgG antibodies to Tdap vaccine antigens (PT (Pertussis Toxin), FHA (Filamentous Hemagglutinin), PRN (Pertactin), tetanus, diphtheria) as measured by ELISA in pregnant women one month after receipt of BOOSTRIX or Td, at the time of delivery, and 6 months after delivery.
- Infant humoral immunity: GMC of serum IgG antibodies to Tdap vaccine antigens (PT, FHA, PRN, tetanus, diphtheria) as measured by ELISA at birth and prior to receipt of first DTwP (approximately 6 weeks of age) among infants born to women vaccinated with BOOSTRIX compared to Td.
- Placental antibody transfer: The geometric mean ratio (GMR) of maternal and infant-specific Tdap-specific antibodies (PT, FHA, PRN, tetanus, diphtheria) as measured by ELISA at delivery after intrapartum receipt of BOOSTRIX versus Td.
- Interference with infant responses among infants whose mothers received intrapartum BOOSTRIX compared to Td: GMC of antibodies to DTwP vaccine antigens (PT, FHA, PRN, Fimbriae 2 (FIM2), Fimbriae 3 (FIM3), tetanus, diphtheria) as measured by ELISA one month after the first dose of DTwP (~10 weeks of age, ½ of infants), one month after the third dose of DTwP vaccine (~18 weeks of age, ½ of infants), and at 6 months of age.

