Infants born to the pregnant subjects will have 4 study visits: at birth, at approximately 6 weeks of age (day of first DTwP), at approximately 10 or 18 weeks of age (one month after first or third dose of DTwP, respectively), and at 6 months of age.

Blood and colostrum/breast milk samples for immunologic assessments will be collected as described below:

- Pregnant subject: approximately 30 mL of blood will be collected on Study Day 1 (prior to vaccination), Study Day 31 (one month after vaccination), at delivery, and at 6 months postpartum in all women.
- Infants: up to 30 mL of umbilical cord blood will be collected at delivery and 5 mL peripheral blood will be collected at 6 weeks (prior to first dose of DTwP), either the 10-

week or 18-week (per randomized study schedule), and 6 months of age in all infants. If cord blood cannot be obtained, 2-5 mL of peripheral blood will be collected by venipuncture within 72 hours of birth, before discharge, when possible. Cord blood is preferred over venipuncture.

- At delivery, and at the 6-week, either the 10-week or 18-week (per randomized study schedule), and the 6-month postpartum visit, a 10-20mL sample of colostrum or breast milk will be collected. When possible, the first breast milk or colostrum collection will occur while the mother and baby are admitted for delivery and postpartum care. When not possible, it may be collected any time within the first 4 days of life.

Safety will be monitored from the time of signing of the ICF until trial termination.

For additional details on study procedures and evaluations and study schedule by type of visit or study visits/days, see [Sections 7](#) and [8](#) and [Appendix A](#).

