- 10-20 mL breast milk will be collected from the mother for antibody measurements.
- Study personnel will collect infant length, weight, and head circumference as well as birth outcomes on the appropriate data collection form.

7.4.2.2.3. 10 or 18 Weeks Postpartum Safety Follow-up Visit, Birth + Day 70 (± 5 d) or Birth + Day 130 (± 5 d): Clinic Visit, Postpartum Women and Infants (Visit 07 or V07)

- Obtain interim medical history of mother and infant, including an assessment for new medical conditions by interview of subjects and note any changes since the previous clinic visit. Study personnel will solicit and record all new congenital anomalies and SAEs on the appropriate data collection form.
- Study personnel will record infant concomitant medications on the appropriate data collection form.

- A targeted physical examination may be performed by a study clinician licensed to make medical diagnoses and listed on the Form FDA 1572 as the site principal investigator or sub-investigator, if indicated based on review of interim medical history. A targeted physical exam may be performed on the mother, infant, or both.
- 5 mL of infant venous blood will be collected for serology and cytokine assessments prior to receipt of DTwP.
- 10-20 mL breast milk will be collected from the mother for antibody measurements.
- Study personnel will collect infant length, weight, and head circumference as well as birth outcomes on the appropriate data collection form.

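### The infant interference samples are timed only from birth, and the secondary per-protocol set has no rule tying them to the DTwP dose they are meant to follow

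*Protocol*

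**What the plan says.** The endpoint is defined by dose. Protocol 3.2.2 asks for antibody GMCs one month after dose 1 in half of the infants and "one month after the third dose of DTwP vaccine (~18 weeks of age, ½ of infants" in the other half. Protocol 4 describes the visit in the same way: "at approximately 10 or 18 weeks of age (one month after first or third dose of DTwP, respectively".

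The visit that supplies the sample (V07) is timed by age. Protocol 7.4.2.2.3 sets it at "Birth + Day 70 (± 5 d) or Birth + Day 130 (± 5 d", and Protocol Table 2 and Appendix A repeat this. Neither document gives a window relative to an actual dose date or a rule for a late dose.

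The draw instruction at V07 covers both halves and names no dose: "5 mL of infant venous blood will be collected for serology and cytokine assessments prior to receipt of DTwP". Protocol Table 2 carries the same condition as a footnote. The objective in Protocol 3.1.2 attaches that idea to one dose and one half only: "either prior to the second dose of the primary DTwP series, at approximately 10 weeks of age".

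DTwP is local standard of care, the pentavalent "vaccine at 6, 10, and 14 weeks of age" (Protocol 2.3.1). After the 6-week visit, infants in the 18-week half have no study visit until V07.

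On the analysis side, Protocol 11.4.1 and SAP 6.3.2 require only a perinatal blood sample for the infant per-protocol set used in primary and secondary analyses. Exclusions for DTwP outside its window and for samples well outside theirs are listed under the exploratory set. SAP Table 12 confirms that they apply to that set alone. Neither window is defined. SAP 7.2 lists both as major deviations to be reviewed for per-protocol exclusion, without limiting them to the exploratory set.

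**The concern.** A sample can be in window under the protocol and still not be what the endpoint says it is. If dose 3 is late, a draw on days 125 to 135 measures the response at some other interval, or the state after dose 2. SAP Tables 23 and 24 would still show it in the row for one month after the last dose, because the SAP has no rule that assigns samples by dose date. Listing 8 has the planned time point and the actual study day, but no dose date.

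Interference with whole-cell DTwP responses is a main rationale for running the trial in Mali (Protocol 2.2). The per-protocol analysis is where a reader would expect mistimed samples to be removed, and for this secondary endpoint it does not remove them.

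**Working it through.** **Inputs.** DTwP at 6, 10 and 14 weeks is days 42, 70 and 98 (Protocol 2.3.1). V06 is day 42 ±5, so days 37 to 47, and is the day of dose 1 (Protocol 4 and 7.4.2.2.2). V07 is days 65 to 75 or days 125 to 135 (Protocol 7.4.2.2.3).

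**The plan's own figure, doses on time.** Interval = draw day − dose day.
- 18-week half: 125 − 98 = 27, 130 − 98 = 32, 135 − 98 = 37 days after dose 3.
- 10-week half: 65 − 42 = 23, 70 − 42 = 28, 75 − 42 = 33 days after dose 1.

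Both agree with one month.

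**Visits in window, later doses at exact 4-week gaps (an assumption).**
- 18-week half: dose 3 falls between 37 + 56 = 93 and 47 + 56 = 103. The interval runs from 125 − 103 = 22 to 135 − 93 = 42 days.
- 10-week half: 65 − 47 = 18 to 75 − 37 = 38 days after dose 1. If dose 2 is given on day 70, draws on days 71 to 75 are in window but come after dose 2.

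**Late dose 3.** Interval = draw day − (98 + delay). The delays are assumptions, because the documents give none.

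| Delay (days) | Draw on day 125 | Day 130 | Day 135 |
|---|---|---|---|
| 0 | 27 | 32 | 37 |
| 7 | 20 | 25 | 30 |
| 14 | 13 | 18 | 23 |
| 21 | 6 | 11 | 16 |
| 28 | −1 | 4 | 9 |
| 35 | −8 | −3 | 2 |
| 38 | −11 | −6 | −1 |

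A draw less than a week after dose 3 first becomes possible at a 21-day delay. A draw before dose 3 needs a delay of more than 27 days on the earliest window day, 32 on day 130 and 37 on the last.

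**What mistimed samples could do (illustration).** Protocol Table 10 gives post-dose-3 PT GMCs of 28.8 (SD 0.68) with maternal Tdap and 43.2 (SD 0.65) without. Half of 133 and 67 is about 67 and 33 infants.
- Log difference: ln(43.2/28.8) = 0.405. Pooled SD is 0.670.
- Standard error: 0.670 × √(1/67 + 1/33) = 0.1425. The 95% half-width is 1.96 × 0.1425 = 0.28.
- Power, normal approximation: Φ(0.405/0.1425 − 1.96) = 0.81.

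Assume that a fraction f of samples in both arms carries no arm difference and that the SD is unchanged. The ratio is then exp(−0.405(1 − f)):
- f = 0.10: ratio 0.69 instead of 0.67, power 0.73
- f = 0.20: ratio 0.72, power 0.62

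**The case against.** The birth anchor works whenever dosing is on time, and the documents give no reason to expect a particular rate of delay. That stands. A reader might infer that the 18-week sample is generally taken days after dose 3 or before it. It is not, unless dose 3 is about three weeks late or more.

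A reader might also infer that sites are told to take the 18-week sample before dose 3. The text does not support that. The draw condition is shared wording: the objective ties it to dose 2 at 10 weeks, and on the 6/10/14-week schedule no DTwP dose is left to give at 18 weeks. The condition simply has no valid meaning there.

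A third tempting reading is that late-dosed BOOSTRIX infants hold more residual maternal antibody and so bias the result toward no interference. This fails, because every infant in this half is drawn at the same age, days 125 to 135. With double-blind allocation, delays are not expected to differ by arm either, and the direction of any distortion is not established.

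The effect on the estimate may be small. At 10% mistimed, the log ratio moves by about 0.04 against a half-width of 0.28, and the trial seeks preliminary estimates rather than a formal test. For infant cytokines, the exploratory per-protocol set already has the exclusions, although undefined. What the objection does not answer is that the secondary per-protocol set lacks them and SAP 7.2 points the other way.

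**Conclusion.** The point holds in a conditional form and should be fixed. It is not a fatal flaw. Three things follow from the text alone:
- The endpoint and the visit use different anchors.
- The before-DTwP condition does not apply to the 18-week half.
- The per-protocol set for the interference endpoint lacks timing exclusions that SAP 7.2 lists without restriction.

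The size depends on how late dose 3 is given, which the documents do not say. There is no problem when dosing is on time, the interval is 13 to 23 days at two weeks late, and it straddles dose 3 at four to five weeks late. The power figures rest on the assumption that mistimed samples carry no arm difference, so they show sensitivity and are not a forecast. That late samples would be tabulated under the post-dose label is inferred from the lack of any rule to the contrary.

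**What to change.** 1. In SAP 6.3.2, 8.2.4 and Table 12, apply the DTwP-timing and sample-window exclusions to the secondary interference per-protocol analysis, define both windows, and bring SAP 7.2 and Protocol 11.4.1 into line.
2. In SAP 8.2.4 and 8.3.4, count a per-protocol sample as one month after dose only if the recorded dose preceded it by an interval stated before unblinding, for example 21 to 42 days. That example covers the 22 to 42 days found above for the 18-week half. It would drop 10-week draws taken 18 to 20 days after dose 1, so the limits may need to be set separately for each half.
3. Keep all samples in the ITT analysis, and report actual dose-to-sample intervals by arm.
4. Reconcile Protocol 3.1.2, 3.2.2, 7.4.2.2.3 and Table 2 so that the before-DTwP draw condition is limited to the 10-week half.

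The cost is SAP wording, a protocol clarification and a few fewer infants in the per-protocol table. No new data are needed, because infant vaccinations are recorded through the day-180 visit (Protocol 6.6). Do not require the 10-week draw at 28 to 35 days after dose 1: dose 2 is due 70 − 42 = 28 days after dose 1, so only the first day of such a window would avoid following an on-time dose 2. Nothing here should change when infants are vaccinated.

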7.5. Final Study Visit

6 months Postpartum Safety Follow-up Visit, Birth + Day 180 (± 7 d): Clinic Visit, Postpartum Women and Infants (Visit 08 or V08)

- Obtain interim medical history of mother and infant. Study personnel will solicit and record all new congenital anomalies and SAEs on the appropriate data collection form.
- Study personnel will record infant concomitant medications on the appropriate data collection form.
- A targeted physical examination may be performed by a study clinician licensed to make medical diagnoses and listed on the Form FDA 1572 as the site principal investigator or sub-investigator, if indicated based on review of interim medical history. A targeted physical exam may be performed on the mother, infant, or both.
- 5 mL of infant venous blood will be collected for serology assessments.
- Approximately 30 mL of venous blood will be collected from the mother for post-vaccination serology and cytokine assays.
- 10-20 mL breast milk will be collected from the mother for antibody measurements.
- Study personnel will collect infant length, weight, and head circumference as well as birth outcomes on the appropriate data collection form.
- Study personnel will discharge mother and infant from study.

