3.1.3. Exploratory

Immunogenicity:

- To assess the effects of maternal age, parity, gestational age (GA) at which the vaccine is given, GA at delivery, and infant birthweight on antibody responses to BOOSTRIX in pregnant women at time of delivery, and in their newborn infants at birth.
- To assess maternal secretory immunity through measurement of breast milk antibodies to Tdap vaccine antigens in women at the time of delivery, at 6 weeks postpartum, at 10 weeks (in ½ of women) or 18 weeks (in ½ of women) postpartum, and at 6 months after delivery.
- To assess the cytokine profile after stimulation in vitro with diphtheria, tetanus and pertussis antigens of peripheral blood mononuclear cells (PBMC) obtained from women before and one month after receiving Tdap or Td.
- To assess the cytokine profile after stimulation in vitro with diphtheria, tetanus, and pertussis antigens of PBMC obtained from infants before the first dose of DTwP (approximately 6 weeks of age) in all subjects, one month after the first dose of DTwP (approximately 10 weeks of age) in ½ of infants, one month after the last dose of DTwP (approximately 18 weeks of age) in ½ of infants, and at 6 months of age in all infants.

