3.2.3. Exploratory

Immunogenicity:

- Maternal immunogenicity cofactors for maternal and neonatal anti-PT antibody responses following intrapartum BOOSTRIX: Maternal age (18-29, 30-39 years old), parity (primiparous vs. multiparous), GA at time of vaccination (14-17, 18-21, 22-26 weeks), GA at time of delivery (28-32, 33-36, 37 or more weeks), and infant birthweight as potential independent associations with PT GMC.
- Maternal secretory immunity: GMC of breast milk IgG and IgA antibodies to Tdap vaccine antigens (PT, FHA, PRN, tetanus, diphtheria) as measured by ELISA in women at the time of delivery, at 6 weeks after delivery, at 10 weeks (in ½ of women) or 18 weeks (in ½ of women) after delivery, and 6 months after delivery after intrapartum receipt of BOOSTRIX versus Td.
- Maternal cytokine responses: Cytokines produced by peripheral blood cells stimulated with DTwP vaccine antigens, as measured by multiplex assays, in women before and one month after receiving Tdap. Cytokines measured will include: Interferon (IFN)- γ , Inerleukin (IL)-10, IL-12p70, IL-12/IL-23p40, IL-13, IL-15, IL-16, IL-17A, IL-1 α , IL-1 β , IL-2, IL-4, IL-5, IL-6, IL-7, IL-8, Tumor Necrosis Factor (TNF)- α , and TNF- β .
- Infant cytokine responses: Cytokines produced by infant peripheral blood cells stimulated with DTwP antigens from infants whose mothers received intrapartum BOOSTRIX versus Td, measured by multiplex assays before the first dose (or umbilical cord blood), one month after the first dose of DTwP (~10 weeks of age, ½ of subjects), one month after the last dose of study vaccine (approximately 18 weeks, ½ of subjects), and at 6 months of age. Cytokines measured will include: IFN- γ , IL-10, IL-12p70, IL-12/IL-23p40, IL-13, IL-15, IL-16, IL-17A, IL-1 α , IL-1 β , IL-2, IL-4, IL-5, IL-6, IL-7, IL-8, TNF- α , and TNF- β .

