- The newborn infant will be enrolled into the study at the time of birth. A targeted physical examination may be performed by a study clinician licensed to make medical diagnoses and listed on the Form FDA 1572 as the site principal investigator or sub-investigator, if indicated based on review of interim medical history. A physical exam performed by the infant's doctor may also provide information, if required, for documentation.
- Axillary temperature, heart rate, respiratory rate, head circumference, length, and weight will be collected from the medical chart of the infant. If not performed as part of routine care, these measurements, except weight may be taken by qualified members of the research team within 7 days of life. Weights will only be recorded when obtained at birth.
- For infants, study personnel will solicit and record on the appropriate data collection form infant AEs, SAEs, and concomitant medications/vaccinations until the day of life 180

visit. Only medically attended AEs will be recorded. Events associated with routine newborn care and health maintenance visits will not be recorded.

- To collect cord blood and to perform physical examination of the mother and newborn at delivery, an on-call team comprised of a study physician and nurse will be posted at the recruitment site close to the delivery room. This team will collaborate with the local on-call team. The team will refer to the study ID or consent form to confirm the identification of the participant.

7.4.2.2.2. 6 Weeks Postpartum Safety Follow-up Visit, Birth + Day 42 (± 5 d): Clinic Visit, Postpartum Women and Infants (Visit 06 or V06)

- Obtain interim medical history of mother and infant, including an assessment for new medical conditions by interview of subjects and note any changes since the previous clinic visit. Study personnel will solicit and record all new congenital anomalies and SAEs on the appropriate data collection form.
- Study personnel will record infant concomitant medications on the appropriate data collection form.
- A targeted physical examination may be performed by a study clinician licensed to make medical diagnoses and listed on the Form FDA 1572 as the site principal investigator or sub-investigator, if indicated based on review of interim medical history. A targeted physical exam may be performed on the mother, infant, or both.
- 5 mL of infant venous blood will be collected for serology and cytokine assessments.

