### 8.3.4. Infant cytokine responses

Summaries and analysis of immunogenicity data will be presented by treatment group for infant cytokine responses prior to first dose of DTwP (or umbilical cord blood), one month after the first dose of DTwP (half of subjects), one month after last dose of study vaccine (half of subjects), and at 6 months of age. Cytokines produced by peripheral blood stimulated with DTwP vaccine antigens will be measured by multiplex assays. Cytokines measured will include IFN- $\gamma$ , IL-10, IL-12p70, IL-12/IL-23p40, IL-13, IL-15, IL-16, IL-17A, IL-1 $\alpha$ , IL-1 $\beta$ , IL-2, IL-4, IL-5, IL-6, IL-7, IL-8, TNF- $\alpha$ , and TNF- $\beta$ . Analysis will include GMCs and corresponding 95% confidence intervals, median, Q1, Q3, minimum, and maximum for each cytokine at each time point as well as the change in cytokine concentration from baseline to each time point ([Table 35](#) and [Table 36](#)).

Concentrations of each cytokine will be plotted over time by treatment group in [Figure 165](#), [Figure 166](#), [Figure 167](#), [Figure 168](#), [Figure 169](#), [Figure 170](#), [Figure 171](#), [Figure 172](#), [Figure 173](#), and [Figure 174](#). The GMCs and 95% confidence intervals of the concentrations of each cytokine will be presented over time by treatment group in [Figure 185](#), [Figure 186](#), [Figure 187](#), [Figure 188](#), [Figure 189](#), [Figure 190](#), [Figure 191](#), [Figure 192](#), [Figure 193](#), and [Figure 194](#). The change in cytokine concentration will be plotted for each post-

---

baseline time point by treatment group in [Figure 205](#), [Figure 206](#), [Figure 207](#), [Figure 208](#), [Figure 209](#), [Figure 210](#), [Figure 211](#), [Figure 212](#), [Figure 213](#), and [Figure 214](#).

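### The 6-month visit instruction does not assign infant blood to cytokines although the objective, endpoint and SAP plan them, and the infant cytokine baseline has no rule for choosing between the 6-week sample and cord blood

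*Protocol*

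**What the plan says.** **The 6-month infant sample.** Protocol 7.4.2.2 assigns the 6-week draw (V06) to both assays: "5 mL of infant venous blood will be collected for serology and cytokine assessments". It does the same at 10 or 18 weeks (V07): "5 mL of infant venous blood will be collected for serology and cytokine assessments prior to receipt of DTwP". For the final visit (V08), Protocol 7.5 reads "5 mL of infant venous blood will be collected for serology assessments".

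The exploratory objective in Protocol 3.1.3 nevertheless plans infant cytokines "at 6 months of age in all infants". The endpoint in Protocol 3.2.3 ends its list of time points with "one month after the last dose of study vaccine (approximately 18 weeks, ½ of subjects), and at 6 months of age". SAP 3.2.3, 4.5.2 and 8.3.4 repeat the 6-month point. The SAP Table 35 shell has a 6-month level block and a 6-month change block for each cytokine, and Table 36 repeats it for the per-protocol population.

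**The 6-month maternal sample.** In the same section of the protocol: "Approximately 30 mL of venous blood will be collected from the mother for post-vaccination serology and cytokine assays". The maternal cytokine endpoint (Protocol 3.2.3, SAP 8.3.3, Table 33) covers only the samples before and one month after vaccination.

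**The infant baseline.** The objective and Table 35 place it before the first DTwP dose, at about 6 weeks. SAP 8.3.4 gives it as "prior to first dose of DTwP (or umbilical cord blood". The same alternative is in the Protocol Summary outcome measures, Protocol 3.2.3, SAP 3.2.3 and SAP 4.5.2. SAP 8.3.4 then calculates change from baseline at every later time point.

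**The concern.** The infant cytokine analysis needs cells stimulated in vitro, and serum contains none. If the 6-month tube is processed for serum alone, the assay cannot be done later. Six months is also the only infant time point after DTwP at which every infant is meant to contribute; 10 and 18 weeks each use half.

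The baseline matters because every infant change score is measured from it. Cord blood at birth and venous blood at 6 weeks differ in the infant's age and in the source of the cells. With no stated precedence, two analysts could follow the SAP correctly and report different changes for the same infant.

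**Working it through.** No power or sample-size figure is involved. The check sets the visit instructions beside the planned analyses and adds simple counts.

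**1. Purpose of each draw against the cytokine plan**

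| Draw | Assays named in the visit section | Cytokines planned there? |
|---|---|---|
| Infant, 6 weeks (V06) | serology, cytokines | yes, all infants |
| Infant, 10 or 18 weeks (V07) | serology, cytokines | yes, half at each |
| Infant, 6 months (V08) | serology | **yes, all infants** |
| Mother, Day 1 | serology, cytokines | yes |
| Mother, Day 31 | serology, cytokines | yes |
| Mother, delivery (V05) | serology | no |
| Mother, 6 months (V08) | serology, cytokines | **no** |

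The stated purpose matches the planned analyses at every draw except the two at V08. The maternal delivery draw shows that the protocol names serology alone where no cytokine analysis is planned, so the wording carries information.

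**2. Blood volume.** Protocol Table 2 gives 5 mL at each of V06, V07 and V08: 5 + 5 + 5 = 15 mL. Adding up to 5 mL at birth when there is no cord blood gives 20 mL, the stated maximum. The 6-month blood is therefore drawn; what is missing is its assignment to cytokines.

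**3. Outputs that depend on that assignment.** 18 cytokines × 2 blocks (6-month level, change to 6 months) = 36 blocks in Table 35 and 36 in Table 36, 72 in all.

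**4. What the other post-DTwP points could supply.** At 6 months the planned numbers are 133 and 67 before attrition. At 10 or 18 weeks they are about half, 66.5 and 33.5 on average. For the same SD, the log-scale interval for the difference between arms widens by

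√[(1/66.5 + 1/33.5) / (1/133 + 1/67)] = √(0.04489 / 0.02244) = √2 ≈ 1.41.

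**5. Interval covered by a change score** (nominal days: cord blood 0, V06 42, V07 70 or 130, V08 180)

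| Change to | From 6-week baseline | From cord-blood baseline |
|---|---|---|
| 10 weeks | 70 − 42 = 28 days | 70 days |
| 18 weeks | 130 − 42 = 88 days | 130 days |
| 6 months | 180 − 42 = 138 days | 180 days |

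The two baselines are 42 days apart but share one row of Table 35. No section says when cord blood replaces the 6-week sample, which prevails if both exist, or whether they are reported separately. The delivery visit does not assign the cord blood to cytokines either.

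**The case against.** The strongest reply is that this is one missing word. Section 7.5 does not say that the sample is for serology exclusively. Protocol section 4 describes all samples as being for immunologic assessment, and the objective, the endpoint and several SAP sections state the 6-month infant cytokine plan. Specimen handling is delegated to the Manual of Procedures (Protocol 8.2.3.1), which may already require the cells to be processed. This stands to the extent that the loss is conditional. It does not remove the conflict: the visit section tells the site what to do, and it differs from the two preceding infant visits on exactly this point.

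On the baseline, cord blood can fairly be read as a fallback. The 6-week sample is scheduled for every infant and is assigned to cytokines, and both sources precede DTwP. That also stands; what is missing is a rule.

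A reader might infer that the infant and maternal V08 instructions were exchanged. The documents do not show this. The maternal line follows the Day 31 wording, so carry-over from that visit explains it at least as well. A reader might also infer that every infant change score is compromised. Only infants given a cord-blood baseline are affected, and nothing suggests that their share would differ by arm.

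**Conclusion.** The point holds as two inconsistencies to be reconciled. First, Protocol 7.5 does not assign the 6-month infant sample to cytokines although the analysis plan depends on it. If the instruction is followed literally, 36 blocks in each of Tables 35 and 36 cannot be filled, for at most 200 infants. It would be too strong to say that these data will be lost: that assumes the Manual of Procedures follows the visit wording, and the Manual is not available here.

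Second, the baseline definition permits two sources 42 days apart in one change score without a precedence rule. The share of infants concerned is not given and cannot be derived.

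Both matters are confined to an exploratory analysis summarised by GMCs with confidence intervals, quartiles and ranges, with no test planned. The primary and secondary analyses are unaffected. The correction is still worth making because it is cheap, whereas cells that were not processed cannot be recovered.

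**What to change.** 1. In Protocol 7.5, name cytokines alongside serology for the infant sample, as at V06 and V07, and check that the Manual of Procedures agrees. The 5 mL is unchanged and no draw or visit is added; the cost is the laboratory processing of up to 200 samples. If 6-month infant cytokines are not wanted, remove them from the objective, endpoint, SAP text and table shells instead.
2. Reconcile the 6-month maternal cytokine collection: remove it from Protocol 7.5, or add a matching endpoint and SAP analysis.
3. Define the baseline for infant change scores as the 6-week pre-DTwP sample in every place that now allows cord blood: the Protocol Summary outcome measures, Protocol 3.2.3, and SAP 3.2.3, 4.5.2 and 8.3.4. The objective and Table 35 already say this. Changing only SAP 8.3.4 would leave the SAP in conflict with itself and with the protocol.
4. If cord-blood cytokines are assayed, report them as a separate time point in Tables 35 and 36, and name the assay at the delivery visit.

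The cost of items 3 and 4 is wording and an extra table row. The statistical cost is that infants without a 6-week sample leave the change analysis; their number should be reported by arm.
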